1 SYNOPSIS

Protocol title: A Randomized, Open label, Parallel-group, Single Dose Regimen, Phase 2a

Study, to Investigate the Clinical and Parasiticidal Activity and the

Pharmacokinetics of 3 dose levels of Artefenomel (OZ439) given in combination with Ferroquine (FQ) and FQ alone, in African Patients with Uncomplicated

Plasmodium falciparum Malaria

Short title: A Randomized, Open, Parallel-group, Single Dose, Phase 2a Study, to Investigate

the Clinical and Parasiticidal Activity and the Pharmacokinetics of 3 dose levels of Artefenomel in combination with Ferroquine (FQ) and FQ alone, in African

Patients with Uncomplicated Plasmodium falciparum Malaria

Rationale:

Plasmodium falciparum (P. falciparum) malaria remains a deadly endemic parasitic disease, with 212 million new cases and over 429,000 deaths reported in 2015. World Health Organization (WHO) guidelines recommend that artemisinin-based combination therapies (ACT) are used to treat uncomplicated P. falciparum malaria, which is administrated in a 3-day regimen. Sanofi and Medicines for Malaria Venture (MMV) are co-developing a fixed dose combination (FDC) of FQ and artefenomel (OZ439) for a single dose treatment of uncomplicated malaria in adults and children. Per Food and Drug Administration (FDA) guidance for co-development of 2 new investigational drugs for use in combination, it is recommended to demonstrate the contribution of each individual component to the effect of the combination. This phase 2a study will test clinical and parasiticidal activity, pharmacokinetics (PK) and safety of 3 doses of OZ439 associated with a fixed dose of FQ and FQ alone.

Objectives and endpoints

Objective Endpoint Primary To show the contribution of OZ439 to the clinical and parasiticidal effect of OZ439/FQ combination by analyzing exposure-response of OZ439 measured by Day 28 polymerase chain reaction (PCR)-corrected adequate clinical and parasitological response (ACPR) for the effect and the area under the concentration time curve up to infinity (AUC) of OZ439 as PK predictor

Secondary

- To evaluate the dose response of OZ439 combined with FQ on PCR-corrected and crude Day 28 ACPR
- To evaluate the dose-response of OZ439 combined with FQ on selected secondary endpoints
- Day 28 PCR-corrected ACPR
- Day 28 crude ACPR
- Parasitemia at baseline then every 6 h during the first 36 h then at 48 h and every 24 h until Day 7
- Observed parasite reduction rate (PRR) at 24 h, 48 h, and 72 h

Clinical Trial Protocol ACT14655 – artefenomel/ferroquine

13-Nov-2017 Version number: 1

- Time to 99% parasite reduction
- Time to parasite clearance
- Parasite clearance rate
- Time to recrudescence or re-infection
- time elapsed below limit of quantification (LOQ) of parasitemia
- Adverse events (AEs) including Serious AEs (SAEs), AEs of Special Interest (AESIs) and Treatment Emergent AEs (TEAEs)
- Clinical laboratory tests (including liver function tests [LFT]), vital signs, and electrocardiogram (ECG) including QTc assessment
- Physical examination and clinical signs and symptoms related to uncomplicated *P. falciparum* malaria (fever, dizziness, headache, nausea, anorexia, vomiting, diarrhea, itching, urticaria, skin rash, abdominal pain, joint pain, muscle pain, palpitations, sleep problems, confusion, hearing problems, vision problems, and fatigue).
- Concentrations of OZ439 in plasma, and of FQ and SSR97213 in blood at specific time points
- PK parameters for OZ439 in plasma, and for FQ and SSR97213 in blood, including:
 - maximal concentration (C_{max})
 - time to reach C_{max} (t_{max})
 - concentration at 168 h post dose (C_{168h})
 - AUC
 - terminal half-life (t_{1/2})
 - area under the concentration time curve from T0 to Day 28 (AUC_{0-Day28}) for FQ and SSR97213 only

To characterize the PK of OZ439 in plasma, and of

FQ and its active metabolite SSR97213 in blood

To evaluate the safety and tolerability of different

dosages of OZ439 in combination with FQ and FQ

Overall design:

A phase 2a, randomized, open label, parallel-group study, single-dose regimen, testing 3 dose levels of OZ439 given in combination with FQ and FQ alone in participants with uncomplicated *P. falciparum* malaria. Adults up to 69 years old and adolescents as of 14 years old will be included in 4 parallel arms in a 1:1:1:1 randomization ratio. Randomization will occur the day of or up to 1 day after screening procedures.

Participants will receive one of the 4 treatments: FQ 400 mg alone or combined with OZ439 300 mg, 600 mg, or 1000 mg.

Participants will be hospitalized for the first 48 hours or up to 4 days or longer upon investigator's judgment.

Number of participants:

Participants will be screened to achieve 140 randomly assigned to study treatment and 120 evaluable participants for an estimated total of 30 evaluable participants per treatment group.

Details on sample size determination are provided in Section 10.1.

Evaluable participants are defined as all randomized participants with parasitologically confirmed malaria at baseline, who received the single administration of investigational medicinal product (IMP) and having parasitemia data post-randomization (Section 10.2).

Treatment groups and duration:

Study will last for up to 32 days for each participant:

- Up to 1 day screening period before the single-dose treatment
- 5 days of post-treatment surveillance, including 2 to 4 days hospitalization
- 24±2 days follow-up

Study treatments

Study treatments include FQ (all participants including arm A), OZ439 + FQ (participants of study arms B, C, and D), and a rescue therapy (all participants).

IMP: FQ (SSR97193)

- Formulation: 100 mg capsules
- Route of administration: oral
- Dose regimen: single dose of 400 mg given before OZ439

IMP: Artefenomel (OZ439)

- Formulation: sachet of 300 mg, 400 mg, and 600 mg of OZ439-alpha tocopherol polyethylene glycol 1000 succinate (TPGS) formulation + sachet of sucrose
- Route of administration: oral
- Dose regimen: single dose given after FQ, depending on the treatment arm: 0 mg for arm A, 300 mg for arm B, 600 mg for arm C, and 1000 mg for arm D

Noninvestigational medicinal products: rescue therapy

- A rescue treatment will be systematically administered at Day 28 for participants who reach Day 28 without having received a rescue medication
- The use of established anti-malarial drug combination per WHO recommendations and per local regulations and the choice of the best therapeutic option is left at investigator's decision.

Statistical considerations:

• **Primary analysis:** Logistic regression with p: probability of a response in PCR-corrected ACPR at Day 28 and OZ439 AUC and FQ AUC_{0-Day28} (SSR97213 AUC_{0-Day28} will be considered also) and baseline parasitemia as covariates will be fitted. The Wald test will be used to test the OZ439 exposure effect on PCR-corrected ACPR at Day 28.

Analysis of secondary endpoints:

Dose effect analysis:

A generalized multiple comparison procedures-modeling (MCP-Mod) approach will be used with PCR-corrected and crude ACPR at Day 28. Both linear and log model will be fitted. Then the dose response signal will be tested via contrasts based on dose-response shape.

Clearance rate estimation according to worldwide antimalarial resistance network (WWARN) (1).

- Other activity endpoints:

Cox model will be used for time to event endpoints with OZ439 doses and parasitemia at baseline as covariates, potential interaction will be explored.

Mean values or percentage of participants, per treatment arm, reaching each of the secondary endpoints, will be calculated according to the type of endpoint (quantitative or qualitative) with the corresponding 95% confidence interval (CI).

Safety analyses will be descriptive.

The on-treatment phase will be defined as the time of the first IMP administration (included) up to Day 28 (included).

The PK parameters for different entities will be estimated through Bayesian analysis using previously developed population PK models.

Descriptive statistics for OZ439, FQ and SSR97213 concentrations and PK parameters (C_{max} , t_{max} , C_{168h} , AUC, and $t_{1/2}$ for all entities, AUC_{0-Day28} for FQ and SSR97213 only) will be provided.

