10.3.1 Efficacy analyses

All efficacy analyses will be performed on the mITT Population. The efficacy analyses are summarized in Table 8.

Table 8 - Efficacy analyses

Endpoint	Statistical Analysis Methods
 	Otatistical Arialysis methods
For primary objective:Day 28 PCR-corrected ACPR	 The exposure-response association of single-dose OZ439/FQ for PCR-corrected ACPR at Day 28 will demonstrate how the probability of a response in PCR-corrected ACPR at Day 28 increases with exposure (AUC) to OZ439/FQ. Logistic regression with p: probability of PCR-corrected ACPR at Day 28 and OZ439 AUC and FQ AUC_{0-Day28} (SSR97213 AUC_{0-Day28} will be considered also) and baseline parasitemia as covariates will be fitted.
	 Results of logistic regressions of PCR-corrected ACPR on exposure will be provided in a summary table including odds ratio estimates, the corresponding 95% Wald CIs and p-value.
	 Frequency table for Day 28 PCR-corrected ACPR, i.e. proportion, percentage and exact binomial 95% CIs (two-sided by using Clopper-Pearson method for calculating binomial CIs) by treatment arm, will also be provided.
For secondary objectives:	
 Day 28 PCR-corrected ACPR 	 The dose-response exposure-response association of single-dose OZ439/FQ for PCR-corrected ACPR at Day 28 will demonstrate how the probability of a response in PCR-corrected ACPR at Day 28 increases with increasing dose of OZ439/FQ thanks to a logistic regression. Results of logistic regressions of PCR-corrected ACPR on dose will be provided in a summary table including odds ratio estimates, the corresponding 95% Wald Cls, and p-value.
 Parasitemia at baseline then every 6 h during the first 36 h then at 48 h and every 24 h until Day 7 	 Descriptive statistics (number of observations [n], mean, geometric mean, standard deviation [SD], median, first quartile [Q1], third quartile [Q3], minimum, and maximum) for parasitemia data (number of parasites/µL) (raw data and absolute change from baseline) will be displayed at each post-baseline assessment. Time profile plots (Mean ± standard error of the mean) of parasitemia will be provided for each treatment arm, one curve per arm.
Day 28 crude ACPR	 Same analysis using Clopper-Pearson method as for PCR-corrected ACPR will be done on crude ACPR at Day 28. The exposure-response (respectively dose- response) association of single-dose OZ439/FQ for crude ACPR will also be evaluated.

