	A generalized MCP-Mod approach will be used with PCR-corrected and crude ACPR at Day 28. Both linear and log model will be fitted. Then the dose response signal will be tested via contrasts based on dose-response shape. Selection of the model needs investigations which will be detailed in the SAP.

13-Nov-2017 Version number: 1

	served PRR at 24 h, h, and 72 h	•	Descriptive statistics (n, mean, geometric mean, standard deviation, median, Q1, Q3, minimum, and maximum) by treatment arm and time of measurement.
• Pa	rasite clearance rate	•	Parasite clearance estimator established by WWARN (1) will be used to identify the lag phase, clean the data for outliers, and determine the best model (linear, quadratic, cuboidal) to fit the log-transformed parasite data and afterward calculate the following estimate: the parasite clearance rate. Descriptive statistics (median, first Q1, Q3, minimum, and maximum) will be provided for each treatment arm.
• Tin	ne	•	Kaplan-Meier estimators.
-	to parasite clearance	•	For each variable, an overall overview including number of events (frequency and %), 25%, median and 75% quantile with 95% CI (expressed in weeks), cumulative
-	to 99% parasite reduction		incidence of events with 95% CI will be provided in a summary table for all participants.
-	to recrudescence or re-infection	•	Survival curves will be plotted by representing each treatment arm for all participants.
-	elapsed below LOQ of parasitemia	•	Cox model will be used for time to event endpoints with OZ439 doses and parasitemia at baseline as covariates, potential interaction will be explored.
Exploratory		Will be d	escribed in the statistical analysis plan finalized before database lock

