1.6 STATISTICAL MODIFICATIONS MADE IN THE STATISTICAL ANALYSIS PLAN

The primary efficacy population will be the PK/PD population instead of the mITT population stated in the protocol.

A per-protocol [PP] population was added in order to align the analysis population with the primary endpoint of the study. All populations have been further clarified from the protocol definitions

The derivation of the secondary endpoint, Fever clearance time (FCT), has been added. FCT will be assessed by measuring the time from the first dose until the first time that the body temperature dropped and remained <37.5 °C.

Time to 50% parasite reduction (T_{PC50}) will also be calculated in addition to the time to 99% PR.

The evaluation of the relationship between parasitemia (as measured on thick blood film and/or by qPCR) and concentration of OZ439/FQ may be performed in a separate analysis pooling data from different studies and be reported in a separate report.

The terminal half-life ($t_{1/2}$) for OZ439 and ferroquine will not be estimated as this endpoint does not contribute to the objectives of the study.

The definition of baseline to be used for efficacy analyses has been clarified.

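### The SAP drops the protocol's MCP-Mod test without declaring it, leaves the Cox dose models out of its body while its summary table still lists them, and is unclear on how dose is coded in the ACPR dose-response test that it keeps

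*Protocol*

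**What the plan says.** **Protocol, ACPR.** Two dose-response analyses are planned. One is MCP-Mod: "A generalized multiple comparison procedures-modeling (MCP-Mod) approach will be used with PCR-corrected and crude ACPR at Day 28", with linear and log models fitted, after which "Then the dose response signal will be tested via contrasts based on dose-response shape". Table 8 (section 10.3.1) repeats this and passes the detail on: "Selection of the model needs investigations which will be detailed in the SAP". The other, also in Table 8, is a logistic regression: "Results of logistic regressions of PCR-corrected ACPR on dose will be provided in a summary table including odds ratio estimates", with Wald intervals and a p-value. Dose-response is to be evaluated for crude ACPR as well.

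**Protocol, time-to-event.** "Cox model will be used for time to event endpoints with OZ439 doses and parasitemia at baseline as covariates, potential interaction will be explored". The Table 8 row covers time to parasite clearance, time to 99% reduction, time to recrudescence or re-infection, and time below LOQ.

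**SAP, ACPR.** MCP-Mod does not appear. Section 2.4.4.2.1.1 keeps the logistic regression on dose with a Wald test for crude ACPR, and 2.4.4.1.3 applies the same method to PCR-corrected ACPR.

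**SAP, time-to-event.** Sections 2.4.4.2.6 to 2.4.4.2.10 give descriptive and Kaplan-Meier summaries by arm. The efficacy table that closes Appendix B lists Kaplan-Meier and Cox for these endpoints, with no covariates and on the per-protocol population. Sections 2.4.4 and 2.4.4.2 put them on mITT only.

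**SAP, declared changes.** Section 1.5 says that no amendment altered the protocol's statistical section. Section 1.6, headed "STATISTICAL MODIFICATIONS MADE IN THE STATISTICAL ANALYSIS PLAN", records changes such as "The primary efficacy population will be the PK/PD population instead of the mITT population stated in the protocol", the added fever clearance time and the dropped half-life. It mentions neither MCP-Mod nor Cox.

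**The concern.** The protocol assigned the MCP-Mod detail to the SAP, and the SAP neither supplies it nor says that the analysis was withdrawn. The list of changes covers items as small as dropping a PK parameter, so a reader would take its silence to mean that MCP-Mod stands.

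For the time-to-event endpoints, a programmer who follows the SAP body produces no between-dose estimate or test. One who follows the table has a Cox model with no covariates, no interaction and a different population. The secondary objective on dose-response for these endpoints depends on which is followed.

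With MCP-Mod gone, the logistic regression is the only dose-response test left for ACPR. Section 2.4.4.2.1.1 models increasing dose and names one Wald test of the dose effect, yet its output table is to carry a p-value for every dose level. Section 2.4.4.3 applies no multiplicity adjustment. The SAP therefore does not say which p-value answers the objective.

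**Working it through.** **1. Text comparison**

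| Planned in the protocol | SAP body | SAP summary table | Declared in 1.6 |
|---|---|---|---|
| MCP-Mod, PCR-corrected and crude ACPR | absent | absent | no |
| Logistic regression on dose, ACPR | kept (2.4.4.1.3, 2.4.4.2.1.1) | kept, but PP | not applicable |
| Cox with dose and baseline parasitemia | absent (2.4.4.2.6 to 2.4.4.2.10) | named, unspecified, PP | no |

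Time to 99% reduction is a special case. The SAP computes it as log(100)/k from the clearance rate and summarizes it with a linear fixed effect model (2.4.4.2.5), while the table lists it under Kaplan-Meier and Cox.

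**2. The plan's own power figure.** Both documents state power around 90% for the OZ439 exposure test with 30 evaluable per arm. Simulating equation 2 with its stated coefficients, calibrated to the stated arm rates, gives 0.91 to 0.94. The concentration spread is not given, so coefficients of variation of 0.3 to 0.5 (FQ) and 0.3 to 1.0 (OZ439) were assumed. The figure is plausible but not strictly reproducible, and this point does not rest on it.

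**3. Power of the ACPR dose-response tests**

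Inputs: ACPR 72%, 81%, 91% and 97% at 0, 300, 600 and 1000 mg (Protocol Appendix 8; SAP 1.3); 30 evaluable per arm; two-sided 5% Wald test, as in Appendix 8. Assumed: independent binomial counts, no covariates. There were 20,000 simulated trials.

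| Test | Power |
|---|---|
| Logistic, one linear dose term | about 0.87 |
| Four categories, 3-df Wald, 0.5 added to counts | about 0.44 |
| MCP-Mod, linear and log contrasts, one-sided 2.5%, logit scale | 0.65 to 0.75 |
| MCP-Mod, same, proportion scale | 0.87 |

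The MCP-Mod range reflects contrasts and scale that had to be assumed because no document gives them. With all arms at 72%, the linear test rejects in about 4.6% of trials and the 3-df test in about 3%, so part of the gap between 0.87 and 0.44 is conservatism of the categorical Wald test.

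**4. Separation in the 1000 mg arm**

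The odds ratio against 0 mg has no finite maximum likelihood estimate when the 1000 mg arm has no failures:

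P(no failures) = 0.97^30 = 0.40

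The figure is sensitive to the rate. The SAP's mITT rule counts losses, withdrawals and most reinfections as failures, so the mITT rate may be below 97%. At an assumed 95% it is 0.95^30 = 0.21; at 90% it is 0.90^30 = 0.04.

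For 1000 mg against 0 alone, power is 0.38 to 0.39 if trials without a finite estimate count as non-significant, and about 0.70 with 0.5 added to each count.

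**The case against.** A reader might infer that the dose-response objectives lose their pre-planned tests, or that the SAP swapped MCP-Mod for a weaker logistic regression. The documents do not support this for ACPR. The logistic regression on dose with Wald inference was already in protocol Table 8 and the SAP keeps it, so one of two planned analyses is missing.

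Nor is Cox simply deleted, since the summary table names it. The SAP body also gives dose-wise information: quartiles and event probabilities with confidence intervals by arm, and geometric means by dose group for time to 50% and 99% reduction. What it lacks is a between-dose hazard ratio or test.

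A reader might also set 0.87 for a trend test against 0.38 or 0.39 for 1000 mg versus 0 and blame the loss of MCP-Mod. That does not follow. The lower figure comes mainly from separation, and the SAP does not name that pairwise comparison as its test. With a linear dose term, omitting MCP-Mod costs no power in this scenario.

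Finally, these are secondary phase 2a analyses. All of this stands. It limits the consequence, but leaves the undeclared omission, the conflict between body and table, and the unclear dose coding.

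**Conclusion.** The point holds as a reconciliation and specification defect in the secondary analyses. The primary exposure-response analysis is not affected.

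- **MCP-Mod:** omitted from the SAP and undeclared. No loss of ACPR dose-response power is shown if dose enters as one linear term.
- **Dose coding:** this is where the size lies, about 0.87 against about 0.44 depending on a choice that the SAP does not make clear. The figures assume the design rates, 30 per arm and no covariates. The design rates are for PCR-corrected ACPR; none are given for crude ACPR.
- **Per-level odds ratios:** the 1000 mg estimate fails in about 40% of trials at a 97% rate, less often at lower rates. The SAP names no remedy.
- **Cox:** a conflict between the SAP body and its table, plus an unspecified model. If the body governs, the protocol's time-to-event endpoints have no between-dose comparison. If the table governs, the model cannot be programmed as written.

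**What to change.** 1. Either restore MCP-Mod for both ACPR endpoints, stating the linear and log shapes, the contrasts, the scale and the alpha, or record its removal in SAP 1.6 with a reason.
2. In SAP 2.4.4.2.1.1, and through it 2.4.4.1.3, state that the dose-response test is the Wald test on a single linear OZ439 dose term. Label any per-level odds ratios descriptive and fit them with a method that handles separation, such as Firth's penalized likelihood.
3. Write the Cox model into the SAP body for the protocol's time-to-event endpoints: OZ439 dose, baseline parasitemia, the interaction to be explored, and one stated population. Say how time to 99% reduction (2.4.4.2.5) is treated, since it is derived from the clearance rate. If Cox is not wanted, delete it from the table and declare that in 1.6.
4. Make the population in the summary table agree with 2.4.4 and 2.4.4.2.

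The cost is SAP text and modest programming before database lock. No new data or participants are needed.

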2 SCHEDULE OF ACTIVITIES (SOA)

		Tı	reat	me	nt P	Peri	iod a	and	post-	treat	ment	surve	illand	ce (D	ays)		F	ollow	-up (l	Days))		
Procedure	Screening (up to 1					0 a					1		2	3	4	5	6	7	10	14 ±1	21 ±	28 ±2	
riocedule	day before Day 0)									Но	urs po	st-dos	е			•				±1	2	工工	Notes
	, .,	0	1	2	4	6	8	12	18	24	30	36	48	72	96	120	144	168					
Visit	1 ^b					2					3		4	5	6	7	8	9	10	11	12	13 ^C	
Informed consent	Х																						
Demography, medical history	Х																						
Inclusion/ exclusion criteria	Х																						
IRT call	Х	Х																				Χ	
Randomization		Х																					
Hospitalization	←=====	====	===	===	====	===	===:	===	====	====	====	====:	=→••••	•••••	•••								All patients hospitalized for 48 h post dosing or up to 4 days in case malaria symptoms and/or parasitemia persist at the end of day 2 or longer upon investigator's judgment
Treatment																							
FQ		Х																					Dosing in fasted
OZ439		Х																					condition (see Section 6.3.1)
Rescue therapy ^d		+	•	••	•••	•••	• •••	•••	• •••	•••	•••	•••	•••	•••	•••	•••	•••	•••	•••	•••	••	Χ	
Prior and concomitant medication	Х	Χ								Х			Х	Х	Х	Х	Х	Х	Х	Х	Х	Χ	

		Trea	atn	nent	Pei	iod	and _l	ost-	treatr	nent	surve	illand	ce (D	ays)		F	ollow	/-up (Days))		
Procedure	Screening (up to 1				06)				1		2	3	4	5	6	7	10	14 ±1	21	28 ±2	
Procedure	day before Day 0)								Но	urs po	st-dos	е		u	I	II.		1	±1	± 2	土乙	Notes
	22,00	0 1	2	2 4	6	8	12	18	24	30	36	48	72	96	120	144	168					
Visit	1 ^b				2					3		4	5	6	7	8	9	10	11	12	13 ^C	
Activity																						
Physical exam & malaria signs & symptoms	Х						Х	_	Х	_	Х	Х	(X)	(X)			Х		_	_	Х	Physical exam to be performed at discharge from the hospital
Height	Х																					
Weight	Х											(X)	(X)	(X)							Х	Weight to be taken at discharge from hospital
Temperature (single) ^e	Х	X	()	Х	Х		Х	Х	Х	Х	Х	Х	Х	Х	Х	Х	Χ	Х	Х	Х	Х	
Asexual & sexual parasite count (thick & thin blood films) ^e	Х]_			Х		Х	Х	Х	Х	Х	Х	Х	Х	Х	Х	Х	Х	Х	Х	Х	Measurement required within 4 hours prior to dosing
qPCR, parasite genotyping, RT- qPCR gametocyte detection sampling ^f	х				Х		х	Х	Х	Х	Х	Х	Х	Х	Х	х	Х	Х	Х	Х	х	- dosing
Safety																						
12-Lead ECG ^g	Х	Х		х	X	Х	Χ		Х			Х	(X)	(X)			Х					72 and 96 h post-dose if participant still hospitalized
Vital signs	Х				X		Χ		Х			Х	(X)	(X)		Х	Х	Χ	Х	Х	Х	Vital signs to be taken at discharge from the hospital
AEs	←====	=====	-==	====	====		====		====	====		====	====	=====			=====	=====	=====	====	\Rightarrow	
Laboratory testing																						
Clinical laboratory safety ^h	Х											Х	(X)	(X)			Х		Х	Х	Х	72 and 96 h post-dose if participant still hospitalized

		Т	rea	tme	ent	Pe	rio	d a	nd p	ost-t	reatn	nent s	surve	illand	e (D	ays)		F	ollow	-up (Days)		
Procedure	Screening (up to 1					06	9					1		2	3	4	5	6	7	10	14	21	28 ±2	
Procedure	day before Day 0)										Ног	ırs po	st-dos	е					11	1	±1	± 2	±2	Notes
	,	0	1	2	4	6	8	3	12	18	24	30	36	48	72	96	120	144	168					
Visit	1 ^b					2						3		4	5	6	7	8	9	10	11	12	13 ^C	
Viral hepatitis serology	Х		1					-																rapid spot test (HAV IgM, HBsAg, HCV Ab), and/or HCV RNA (if known)
Pregnancy test	Х																						Х	Urine beta-HCG is the minimum acceptable test. Result must be confirmed negative prior to dosing.
PK OZ439 ^j		Х	Х	Χ	Х	Х			Х		Х			Х	Х		Х		Х		Х			Not measured in Arm A; Plasma samples
PK FQ (+metabolite) ^j		Х	Χ		Х	Х	()	X	Χ		Х				Х				Х		Х		Х	

- a Day 0 is defined as the day of single dose treatment to comply with WHO guidelines (2).
- b Visit 1 may occur on the same day as Visit 2 provided that all baseline assessments and biology results (including parasitemia and laboratory safety) are obtained before patient randomization.
- c In case of study discontinuation, all assessments planned on Day 28, including rescue therapy administration, should be performed as far as possible.
- d Administered at Day 28 for participants who reach Day 28 without having received a rescue medication. At each contact post-dosing, conditions for treatment failure will be assessed and rescue therapy will be given accordingly. See details in Section 7.7.1.
- e Local thick and thin blood films performed at the site, before Informed Consent signature, according to local standard procedures and within 4 hours prior to dosing, can be used as screening/ pre-dose parasitemia assessments (Section 9.1.1.1) provided that a standard procedure is in place at site and blood films staining is performed according to the study operational manual. Blood films (thick and thin) and temperature measurements need to be confirmed as follows: when 1st parasite clearance and 1st temperature < 37.5 °C, measurements need to be confirmed with second reading 6 to 12 hours after the first measurement (ie, to determine Parasite Clearance and Fever Clearance). The first measurement (if confirmed) will be considered the 'Clearance Time'. Asexual and sexual counts will be measured separately: only asexual count will be used as parasitemia for evaluation of study endpoints. If parasites have not cleared within 72 hours after IMP administration and criteria for rescue medication are not met at 72 hours post-dose, blood films should continue to be taken according to site standard practice (or at minimum every 8 hours) until parasite clearance is shown or until criteria for rescue medication are met (see Section 7.7.1). If these additional blood smears are taken they should be recorded as unscheduled visits in the e-CRF. Axillary temperature should be recorded, if the axillary method is not possible, an alternative route (oral, tympanic, rectal) may be used. Within an individual participant the same method of temperature measure should be used throughout the study.
- f RT-qPCR and qPCR will be performed at all parasitemia time-points (To be collected, according to the schedule and the instructions reported in the study operational manual). Parasite genotyping analysis will be performed on previously collected blood spot sample only in case of a positive blood film after initial parasite clearance: one pre-dose sample and one sample at 18 or 24 hours post dosing. A further sample will be analyzed at the time point at which recrudescence/re-infection occurs (if applicable).
- q Single local ECG reading for inclusion purpose and triplicate central ECG reading for safety evaluation during study.
- h Laboratory safety will be performed locally: hematology, clinical chemistry, and urinalysis (see Appendix 2 for details).

Clinical Trial Protocol ACT14655 – artefenomel/ferroquine 13-Nov-2017 Version number: 1

i Where timepoints coincide, the PK samples should be taken after measurement of vital signs, temperature, and ECG. A PK sample (OZ439 and FQ) should be obtained if possible when QTcF >500 ms or QTcF is prolonged by >60 ms from baseline, or when increased ALT is measured (see Section 9.2). PK samples numbering is detailed in Table 3.

AE: adverse event; e-CRF: electronic case report form; ECG: electrocardiogram; FQ: ferroquine; HAV IgM: hepatitis A immunoglobulin M; HBsAg: hepatitis B surface antigen; HCG: human chorionic gonadotropin; HCV Ab: hepatitis C virus antibody; HCV RNA: hepatitis C virus ribonucleic acid; IMP: investigational medicinal product; IRT: Interactive response technology; PK: pharmacokinetics; qPCR: quantitative polymerase chain reaction; RT-qPCR: quantitative reverse transcription polymerase chain reaction; WHO: World Health Organization

